#### 4.7 Analyses of Key Secondary Efficacy Variables

The key secondary efficacy variables will be tested using the same model as in the primary efficacy analysis. For variables that were only measured at baseline and Week 24 (or the latest visit during the randomized treatment period), the change scores will be reported, and treatment group differences will be tested using two sample t-test.

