#### 4.1.2 Secondary Efficacy Variables

The following variables will be analyzed as secondary endpoints:

- Sociability Factor
- SRS-2 social motivation subscale score
- Stanford Binet-5 Abbreviated IQ (ABIQ)

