#### 4.2 General Modelling Considerations for Efficacy Analyses

Unless otherwise specified, the primary model is mixed model with repeated measures (MMRM), with change from baseline to each post-baseline timepoint for a response variable, functioning (low versus high) as the stratification variable, center as a blocking factor, treatment (oxytocin versus placebo), week as a continuous variable, treatment and week interaction, and baseline value as a covariate, with random coefficients for the intercept and week, with an unstructured structure among the random coefficients. We will investigate the interaction of treatment, week, and functioning and adopt the most parsimonious model as the final model. Distributional assumptions will be examined using residuals. These mixed models could fail to converge or encounter difficulties based on their use of asymptotics. If they do, we will attempt to

simplify the models in order to eliminate the problems, and if necessary, move to analyses that assume compound symmetry, but use a Huynh-Feldt correction if compound symmetry fails.

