#### 4.8 Analyses of Exploratory Efficacy Variables

Exploratory efficacy variables will be analyzed the same way as the primary and secondary efficacy variables.

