# 6. 2 Randomized Double-Blind Treatment Phase: Oxytocin or Placebo (24 weeks; Week 0-Week 24)

#### **Baseline Visit** (Week 0) ~ approximately 3-4 hours

Subjects will complete the following procedures and assessments at the Baseline visit:

- Confirmation of Inclusion/Exclusion criteria
- Review all current medications (concomitant medication log)
- Focused Clinical Physical examination

- Full vital signs (heart rate, blood pressure, temperature)
- Females of childbearing potential will be asked to confirm the date of their last menstrual cycle and confirm contraception use if sexually active
- Females of childbearing potential must have had a negative pregnancy test (either urine or serum) within 2 weeks of baseline visit
- Demographics (age, sex, race, ethnicity, date of birth)
- SLAES (monitoring for adverse events) and suicidality assessment
- Oxytocin Dosing Log
- Social Reciprocity Scale (SRS-2)
- Vineland Adaptive Behavior (Vineland-II Survey Form)
- Caregiver Strain Questionnaire
- Aberrant Behavior Checklist
- PDDBI-SV
- CASI-5(Sprafkin, Gadow et al. 2002; Gadow and Sprafkin 2009)
- CGI-S and baseline description of overall functioning
- Social Skills Therapy Log
- Psychosocial Therapy Log
- Questionnaire Guidance Form
- Social Opportunity Questionnaire
- Reading Mind in Eyes Test (RMET), if cognitively able
- Self-Rating of Social Functioning, if cognitively able
- Medication Diary dispensed to caregiver
- Parent Handout (study drug administration instructions)
- Parent Handout (study drug dosing guidelines)
- Parent Handout (risks)
- Randomization
- GUID Record Form
- For randomization purposes: The Mullen receptive language subscale MUST be completed on subjects who are 5 years, 8 months and younger if the Stanford Binet was completed, this must be done prior to randomization in the database)
- Visual Analogue Scale of Change (Clinician), baseline description of functioning only
- OPTIONAL redraw of mRNA, plasma/salivary oxytocin, and methylation for those subjects who may have had a lengthy time between screening and baseline appointments
- Participants or their caregivers will be taught to administer the nasal spray, alternating nostrils, by the study coordinators who will demonstrate medication administration. The caregivers will be provided with suggestions for how to encourage their children to comply with the procedure including setting up a fun routine and providing rewards.

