## Week 12 ~ approximately 30 minutes-

Subjects will complete the following assessments at the week 12 visit:

- Aberrant Behavior Checklist
- PDDBI-SV
- Questionnaire Guidance Form
- Social Opportunity Questionnaire
- SRS-2

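### SAP 4.7 gives SRS-2 Social Motivation, which has two blinded post-baseline visits, a covariance model that two visits cannot fully identify, and names no workable alternative

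*Combined protocol and SAP*

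**What the plan says.** SAP v2.0 section 4.1.2 lists "SRS-2 social motivation subscale score" as one of three secondary endpoints. Section 4.7 says: "The key secondary efficacy variables will be tested using the same model as in the primary efficacy analysis". The exception in 4.7, a two-sample t-test, is for variables measured only at baseline and week 24.

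Section 4.2 defines the primary model. The response is "change from baseline to each post-baseline timepoint for a response variable", time enters with "week as a continuous variable", and the model is fitted "with random coefficients for the intercept and week, with an unstructured structure among the random coefficients". If the fit runs into difficulty, 4.2 calls first for a simplification, which it does not describe. Only if that is not enough does it move to compound symmetry, with a Huynh-Feldt correction. Section 4.4 sets the target as the treatment effect at week 24, and section 2.3 places all analyses after the blind is broken.

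In protocol v6.0 section 6.2, SRS-2 is collected at baseline and in the list headed "Subjects will complete the following assessments at the week 12 visit". It is collected again at week 24 (section 6.3). It is not listed at weeks 4, 8, 16 or 20. RMET is collected at baseline and weeks 8 and 24.

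For RMET and the other exploratory variables, SAP 4.8 says: "Exploratory efficacy variables will be analyzed the same way as the primary and secondary efficacy variables".

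**The concern.** The primary model suits ABC-SW, which has six post-baseline visits. Section 4.7 carries it over unchanged to an endpoint with two change scores per child. The t-test exception does not apply, because SRS-2 is also measured at week 12.

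With fewer covariance quantities than parameters, the likelihood is flat in one direction, and software may report a singular Hessian or a boundary estimate. Such a report can trigger the simplification rule in 4.2. That rule names no structure, and v2.0 does not require the choice to be made without sight of the treatment result. At stake is whether the week-24 standard error for a secondary endpoint comes from a structure fixed in advance or from one picked after unblinding.

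**Working it through.** The plan states no figure for SRS-2, so there is none to reproduce. The check is a parameter count, followed by the size of the effect if the model is simplified.

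**1. Identifiability.** Write the random-effect covariance as g00 (intercept variance), g01 (covariance) and g11 (slope variance), with residual variance s². For visits at weeks a and b:

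- Var(a) = g00 + 2a·g01 + a²·g11 + s²
- Cov(a,b) = g00 + (a+b)·g01 + ab·g11
- Var(b) = g00 + 2b·g01 + b²·g11 + s²

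For SRS-2 (a = 12, b = 24):

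- V11 = g00 + 24·g01 + 144·g11 + s²
- V12 = g00 + 36·g01 + 288·g11
- V22 = g00 + 48·g01 + 576·g11 + s²

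That is three equations in four unknowns.

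| Variable | Post-baseline weeks | Covariance quantities | Parameters | Rank |
|---|---|---|---|---|
| ABC-SW | 4, 8, 12, 16, 20, 24 | 21 | 4 | 4 |
| SRS-2 | 12, 24 | 3 | 4 | 3 |
| RMET | 8, 24 | 3 | 4 | 3 |

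Example with assumed V11 = 9, V12 = 6, V22 = 16:

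- s² = 2, g00 = 18, g01 = -0.8333, g11 = 0.0625. V11 = 18 - 20 + 9 + 2 = 9; V12 = 18 - 30 + 18 = 6; V22 = 18 - 40 + 36 + 2 = 16.
- s² = 4, g00 = 8, g01 = -0.3333, g11 = 0.0347. V11 = 8 - 8 + 5 + 4 = 9; V12 = 8 - 12 + 10 = 6; V22 = 8 - 16 + 20 + 4 = 16.

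Different components give the same covariance matrix.

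**2. What remains estimable.** With two weeks, linear week by treatment fits the same four cell means as categorical week. The 2x2 matrix V is itself determined. One data set was simulated with 145 per arm, 10% missing at week 24 and the V above (all assumptions). The residual variance was fixed in turn at 0.1, 1, 2 and 4. All four fits gave a -2 REML criterion of 1844.319, a week-24 difference of 0.30465 and an SE of 0.50143. The unstructured 2x2 fit gave the same three values.

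**3. If the random slope is dropped.** The model becomes random intercept plus residual, which is compound symmetry with non-negative covariance. Both visits then share the variance (V11 + V22)/2. With complete data and r = SD(week 12)/SD(week 24):

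SE under compound symmetry / true SE = sqrt((r² + 1)/2)

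- r = 0.6: sqrt(1.36/2) = 0.825, about 18% too small
- r = 0.9: sqrt(1.81/2) = 0.951, about 5% too small
- r = 1: 1.00, no distortion

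The documents give no SD for SRS-2 change, so the range of r is an assumption. If r exceeded 1, the SE would be too large.

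Simulation agrees. With variances 9 and 16 (r = 0.75) the formula gives sqrt(1.5625/2) = 0.884. Over 40 simulated two-visit data sets, the mean SE was 0.413 under compound symmetry against 0.468, a ratio of 0.882.

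**4. Huynh-Feldt.** With two visits there is only one difference between visits, so sphericity holds automatically and the correction factor is 1. It does nothing about unequal variances.

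**The case against.** The strongest reply is that the model as written already gives the right answer. Any positive-definite 2x2 matrix can be written in the random-coefficient form, so a converged fit is equivalent to an unstructured 2x2 model. Only the division between random effects and residual is lost, and nobody reports that. In the 40 simulated data sets the specified model converged every time, with a week-24 SE essentially equal to the unstructured one. This stands, and it makes the harm conditional.

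A reader might infer that SRS-2 is bound to end in compound symmetry. The SAP does not say so: simplification comes first, and other simplifications work. Dropping only the intercept-slope covariance leaves three identifiable parameters. In the example, g11 = (16 - 9)/432 = 0.0162, g00 = 6 - 288 × 0.0162 = 1.333 and s² = 9 - 1.333 - 144 × 0.0162 = 5.333 reproduce V exactly.

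A reader might also infer that the nominal 5% test is inflated as the plan stands. Levels of 6.2% to 10.6%, from 2·(1 - Φ(1.96 × ratio)) at ratios 0.951 and 0.825, need both compound symmetry and the assumed r of 0.9 to 0.6. No document supports that range. Nor can the point rest on Kenward-Roger inference: that option appears only in the sample code of the superseded 2013 SAP, and v2.0 names no degrees-of-freedom method.

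Finally, non-identifiability assumes nominal weeks and independent residuals, which the SAP implies but does not state. Under protocol section 6.5, early terminators complete the week-24 questionnaires near their last dose. If actual week were used, such off-schedule values could raise the rank to 4, though identification would be weak.

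**Conclusion.** The point holds in a limited form. For SRS-2 and RMET the specified model has one more covariance parameter than two visits can identify, given nominal weeks and independent residuals. The week-24 contrast is not lost, and a converged fit is sound. The weakness is that a singular or boundary warning would hand the analyst an open choice after unblinding. The obvious choice, dropping the random slope, would make the week-24 SE about 5-18% too small for r between 0.9 and 0.6 (assumed), with no distortion at r = 1, and Huynh-Feldt would not repair it.

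Severity is minor to moderate. One secondary and one exploratory endpoint are affected; the ABC-SW model is identifiable at its six visits and is not touched by this point.

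**What to change.** Add one sentence to SAP 4.7 and refer to it in 4.8: endpoints with two post-baseline visits in the blinded phase (SRS-2, RMET) are analysed by an MMRM with week categorical and an unstructured 2x2 covariance, with the same adjustment for baseline value, functioning and center as in 4.2, and are tested by the treatment contrast at week 24. This uses three covariance parameters for three quantities and gives the result that the current model gives when it converges.

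Falling back on protocol section 10.1 would not serve as well. Its first-order autoregressive structure is identifiable, but at two visits it has one common variance and one correlation, so it also pools the week-12 and week-24 variances.

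The cost is the wording alone: no extra data, visits or participants.

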#### 4.1.3 Exploratory Efficacy Variables

- Clinical Global Impression Severity (CGI-S)
- Clinical Global Impression Improvement (CGI-I)
- CGI-I will be analyzed as an endpoint mean instead of change from baseline.
- ABC subscales for irritability, stereotypy, hyperactivity, and inappropriate speech
- PDDBI-SV total score
- Caregiver strain questionnaire (CSQ) and its subscales
- Vineland 2 adaptive behavior composite score, and domain scores for daily living skills, communication and socialization. Motor skills will not be analyzed since it is only valid in young children
- Reading the Mind in the Eyes test (only in individuals with fluent speech and understanding of basic emotions)

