- 10. Added that the full analysis set will only include participants who have both a baseline and post-baseline ABC-SW, rather than just a post-baseline assessment of the primary outcome. (This reflects deletion of SF as a primary outcome measure.)
- 11. Specified that the demographics and baseline symptom measures will reflect only the full analysis set.
- 12. Clarified that age will reflect age at time of baseline visit rather than screening since there was often a lag of several months between screening and baseline for the early participants in the trial due to issues with study drug.
- 13. Deleted reporting of psychiatric history.
- 14. Will no longer adjust for multiplicity
- 15. Eliminated the following exploratory efficacy measures: Calibrated ADOS severity score, PDD-BI subscales replacing with PPD-BI screening version.
- 16. Eliminated Vineland 2 two domain composite score and maladaptive behaviors subscales, as well as measures listed in item 3.( above) from exploratory efficacy variables.
- 17. In Section 4.2, eliminated age group as a stratification variable, eliminated evaluation of two kinds of models instead using a mixed model with repeated measures (MMRM)
- 18. Specified thresholds for conducting sensitivity analyses for missing data.
- 19. Provided more detail related to SAS programming for primary analyses.
- 20. In Section 4.6 of SAP deleted examination of *OXTR* gene methylation and instead added examination of baseline serum oxytocin level.
- 21. Section 4.7 of SAP, removed bonferroni correction using simple two sample t-test instead
- 22. Error in section 4.8 of final SAP. Exploratory efficacy variables were analyzed in the same way as the key secondary efficacy analyses.
- 23. Section 5.1 changed severity of TEAEs to intensity paralleling changes in the SLAES.
- 24. Section 6, eliminated use of two primary outcomes.

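### SAP 4.7 tests ABIQ and other outcomes with one post-baseline score by an unadjusted t-test on change, dropping the covariates that SAP 4.2 uses elsewhere

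*Combined protocol and SAP*

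**What the plan says.** SAP v2.0 section 4.2 sets the default efficacy model for change from baseline. Besides treatment, week and their interaction it has "functioning (low versus high) as the stratification variable, center as a blocking factor". The starting score enters too, as the section's list shows: "and baseline value as a covariate".

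Section 4.7 applies the primary model to the key secondary variables and then makes an exception. It covers variables "only measured at baseline and Week 24 (or the latest visit during the randomized treatment period"). In that case no model is fitted; instead, section 4.7 states, "the change scores will be reported, and treatment group differences will be tested using two sample t-test". No covariate is named.

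The schedule of events in protocol v6.0 shows which variables fall under the exception:

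- **Secondary (SAP 4.1.2).** "Stanford Binet-5 Abbreviated IQ (ABIQ") is the only one. The Stanford Binet is scheduled at screening and week 24. SRS-2 also has week 12, and the ABC and PDDBI-SV, which form the Sociability Factor, are collected every four weeks, so those two endpoints keep the adjusted model.
- **Exploratory (SAP 4.1.3).** The Vineland scores and the "Caregiver strain questionnaire (CSQ) and its subscales" are scheduled at weeks 0 and 24 of the double-blind phase. Section 4.8 says: "Exploratory efficacy variables will be analyzed the same way as the primary and secondary efficacy variables". Item 22 of the SAP summary of changes makes the route clearer: "Exploratory efficacy variables were analyzed in the same way as the key secondary efficacy analyses".

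Item 21 of the same summary discloses the move to a t-test but gives no statistical reason for it.

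**The concern.** With a single post-baseline score there is nothing for the repeated-measures terms to do, so the 4.2 model cannot be fitted as written. That is a reason to drop week and the random coefficients. It is not a reason to drop baseline value, functioning and center.

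A change score subtracts the baseline but does not model it. Unless the correlation between the two scores is close to 1, part of the variance of change is still predictable from baseline, and the t-test leaves it in the error term. Functioning is also a randomization stratum and, under protocol section 4.5.1, is partly defined by nonverbal IQ, so it is a natural covariate for ABIQ.

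At stake is precision on one named secondary endpoint and some exploratory ones. ABIQ would also be analysed with a different covariate set from the Sociability Factor and SRS-2. There is no excess false-positive risk.

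**Working it through.** **The plan's own figure.** SAP section 6 gives no sample size or power for ABIQ, Vineland or caregiver strain. Its only calculation is for ABC-SW: difference 5, SD 9, two-sided alpha 0.05, power 90%, 71 per group. The formula n = 2(1.960 + 1.282)² × 9²/5² gives 68.1, so 69; the noncentral t gives 69.06, so 70. Power at 71 is 90.8%. The stated figure is reproduced to within 2.

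**Inputs**

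- N = 290, or 145 per arm (SAP section 6; 1:1 allocation, section 1.3).
- Two-sided alpha 0.05 (SAP section 2.2).
- Six centers (protocol summary), hence 5 center parameters. With baseline and functioning, 7 covariate parameters.
- Correlation rho between baseline and Week 24: not in the documents. Assumed 0.5, 0.7, 0.9 and 0.95, with equal variances s² at both times.
- Share of change variance explained by the strata (R²): not in the documents. Assumed 0.05 and 0.10.

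**Step 1: baseline adjustment, large sample.** Var(change) = 2(1 − rho)s². ANCOVA residual variance = (1 − rho²)s². Their ratio is (1 + rho)/2, and the CI width changes by its square root. The effect for which the t-test has 80% power at 145 per arm is 0.330 SD of change. Power under ANCOVA is then taken from the noncentral t with 7 fewer degrees of freedom.

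| rho | variance ratio | CI narrower by | power (t-test 80%) |
|---|---|---|---|
| 0.5 | 0.750 | 13.4% | 89.9% |
| 0.7 | 0.850 | 7.8% | 86.0% |
| 0.9 | 0.950 | 2.5% | 82.0% |
| 0.95 | 0.975 | 1.3% | 81.0% |

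**Step 2: charge for chance covariate imbalance.** Multiply the variance by 1 + k/(N − k − 3). Functioning is balanced by the stratified randomization, so k = 6 for the full 4.2 set (baseline and 5 center terms) and k = 1 for baseline and functioning only. Center is assumed to explain nothing, which is the least favourable case for including it.

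| rho | full 4.2 set, N = 290 (factor 1 + 6/281 = 1.0214) | power | full set, N = 200 (1 + 6/191 = 1.0314) | baseline and functioning, N = 290 (1 + 1/286 = 1.0035) |
|---|---|---|---|---|
| 0.5 | 12.5% | 89.3% | 12.0% | 13.2% |
| 0.7 | 6.8% | 85.2% | 6.4% | 7.6% |
| 0.9 | 1.5% | 81.2% | 1.0% | 2.4% |
| 0.95 | 0.2% | 80.2% | −0.3% | 1.1% |

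Entries other than power are the percentage by which the CI narrows. N = 200 is an assumed lower case. For ABIQ, 290 is an upper bound: children tested with the Mullen have no ABIQ, and IQ testing is not among the early-termination procedures in protocol section 6.5.

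**Step 3: type I error of the t-test.** If the strata explain a share R² of change variance, stratified randomization removes that share from the true variance of the treatment difference, but the t-test still counts it. Actual size = 2[1 − Φ(1.96/√(1 − R²))], which is 0.044 at R² = 0.05 and 0.039 at R² = 0.10.

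**Simulation check** (3,000 trials per setting, 290 children, six strata, blocks of 2 or 4, six uninformative centers). Mean CI width of ANCOVA relative to the t-test was 0.876, 0.932, 0.985 and 0.998 for the four values of rho, in line with step 2. With R² = 0, type I error was 0.048–0.051 for the t-test and 0.050–0.052 for ANCOVA. With R² of 0.05–0.10 it was 0.041–0.047 and 0.048–0.059; the Monte Carlo standard error is about 0.004.

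**The case against.** Section 4.2 yields wherever another section specifies something else. Section 4.7 does so, and the summary of changes says so openly. This is a declared exception, not a contradiction, and a valid test has been chosen. No power target exists for these outcomes. The gain rests on assumed correlations and shrinks to nothing, or slightly below, at rho 0.95 with 100 per arm. Nor is the full covariate set the most efficient one: if center explains nothing, baseline and functioning alone do better at every rho. The conservatism in step 3 concerns all six strata, so if age group drives it, adjusting for functioning does not remove it. The simulated type I errors are too noisy to establish that conservatism independently of the formula. The reach to Vineland and caregiver strain depends on reading 4.8 together with the summary of changes.

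All of this is fair, and it limits the point to efficiency. It does not explain why covariates already collected, and used for the other two secondary endpoints, are dropped for the third. Nor should a correlation near 0.95 be presumed for ABIQ. Its baseline is the screening score, the protocol change summary records that up to 18 months between screening and baseline was allowed, and protocol v6.0 removed the requirement to test within one month of baseline. A longer interval generally lowers the correlation, though the documents do not show by how much.

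**Conclusion.** The concern holds as a matter of efficiency. The plan gives up a moderate amount of precision if the correlation is 0.5 to 0.7 (CI wider than it need be, with 12.5% to 6.8% to be gained at 145 per arm) and almost none if it is 0.9 or higher. These figures assume equal variances at the two times and an uninformative center, and for ABIQ the usable sample will be smaller than 290. The t-test remains valid, and is mildly conservative if the strata predict change. The primary analysis is not affected.

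The absence of age group is not specific to 4.7, because 4.2 omits it too. The change should be made because it is nearly free and aligns ABIQ with the other secondary endpoints. The existing test is not wrong.

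**What to change.** In section 4.7, and for the same kind of variable under section 4.8, replace the t-test with:

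*ANCOVA of change from baseline to Week 24 (or the latest visit during the randomized treatment period) on treatment, baseline value, functioning and center, reporting the adjusted treatment difference with its 95% CI. For ABIQ the baseline value is the screening score.*

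Keeping the latest-visit clause means that the week 24 questionnaires sent to families at early termination (protocol section 6.5) still count for Vineland and caregiver strain. Center is included to match 4.2; leaving it out is defensible, since it was not a stratification factor. Age group may be added because randomization was stratified by it, with a note that 4.2 omits it. The t-test can stay as a supportive analysis.

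The cost is one sentence and one model call. It uses 7 of at most 288 degrees of freedom (9 with age group). No new data are needed and none are dropped.
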